### 4. Design & Procedures

**a. Design and Setting.** A randomized controlled designed will be used to evaluate the effect of *bundled diaper care* on overall infant and skin health. Infants will be recruited from the Level IV Intensive Care Nursery (ICN) at Duke University Hospital. The ICN is a Level IV, 67-bed nursery and one of the area's leading referral centers for infants born prematurely. The

Duke ICN has an average daily census of 90% and annually admits 150 VLBW infants. The ICN practices individualized developmental care with standard bundled care intervals that vary based upon an infant's birth weight and feeding status (every 3, 4, or 6 hours). Infants who are admitted or transferred to one of the ICN three stepdown units will also be considered if eligible and will continue to receive the intervention when transferred including the Special Care Nursery at Durham Regional Hospital. The principal investigator has been a clinical nurse specialist affiliated with the ICN since 1993 and has the support of the nursery medical and nursing team to conduct this research including the Division of Neonatology, the ICN Intensive Care Developmental Care Team and the Medical Director.

**b. Participants.** A maximum of 80 VLBW infants will be recruited to ensure at least 25 infants in each study group with complete data. Ten parents of infant participants (5 in each study group) and 10 health care providers will participate in interviews about the acceptability and feasibility of the diapered bundled care intervention. The goal of this study is to enrich the literature with estimation of values and variances of the outcomes measured as well as how these values change over time. With a total sample size of 50 VLWB infants, we are confident that we will be able establish effect to inform a larger subsequent study. Because most of the infants are expected to receive care up to 6-weeks, we expect little missing data or participant attrition.

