d. Procedures: A neonatal provider will give approval for participation in the study. Parents will be approached for consent after eligibility screening is completed (≤ 32 weeks gestation). The principal investigator is a clinical nurse specialist and nurse scientist who has been affiliated in the Intensive Care Nursery since 1993. Study personnel will explain the study, allow time for questions, have a parent sign the consent form, and a copy will be given to the parent. Parents will provide consent for their infant's participation in the study and will give permission for themselves to participate in an interview about the study, if selected. Five parents from each group will purposively selected to participate in an interview. Parents will be selected to include parents with infants < 1000 grams at birth and parents with infant ≥ 1000 grams at birth.

[figure not shown]
Following consent, the infant will be monitored until all inclusion and exclusion criteria are met. At that time randomized to an intervention group and data collection will be initiated. The intervention will continue for six weeks at which time collection of data will stop and bundled diapered care will resume according to unit protocol. If the infant no longer meets inclusion criteria the intervention will be discontinued and routine data collection will be discontinued. The exclusion criteria will be noted, e.g. use of diaper cream, and data collection regarding any new illness characteristics or treatments will continue. If an infant requires a diaper change due to a stool or other needed procedure this will be recorded on a bedside card.

Ten nurses will be recruited for participation in interviews around intervention acceptability at the end of the study.

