**Table 1. Data Collection** 

Construct	Measure/	Variable	Time frame		
	Instrument				
	Descriptive data to describe the sample				
Maternal history	EMR 	Age, medical hx. of skin disease,	Enrollment		
Infant characteristics	EMR	GA  , birth weight, diagnoses, antibiotics, delivery mode, lab values as required to describe skin health (e.g. albumin, protein, bilirubin) All bundled care event time frames from study entry to study discharge (expected vs. actual bundled times) During bundled care—respiratory support, changes in support, FiO 2 changes, average Daily FiO 2 , caffeine	Enrollment, 3x/week, or as available		
	Aim 1. Infant	Health			
Bundled care	Observation, videotape & EMR	Specific interventions (e.g. suctioning, positioning, offering pacifier, diapering) Length of bundled care events Time between bundled care events	Observer 3x/week for the 3-hour diaper group and 4s/week for the 6-hour group to allow for one within group comparison; Videotaped 1x/week Daily; retrieved 3x/week		
Physiologic stability	GE monitor	1-minute values of heart rate, respiratory rate and oxygen saturation 15 minutes before and after each observed bundled care event	3x/week for the 3-hour diaper group and 4s/week for the 6-hour group to allow for one within group comparison		
	EMR	# bradycardia events daily	Daily; retrieved 3x/week		
	EMR	# apneic events daily	Daily retrieved 3x/week		
	EMR	# desaturation events daily	Daily retrieved 3x/week		
	EMR	Feeding tolerance (emesis, gastric residual volumeml, feeding interruptions)	Daily retrieved 3x/week		
Weight gain	EMR	Daily weight in grams	Daily retrieved 3x/week		
	Aim 1. Covariates				
Development	EMR	Postmenstrual age (PMA)			
Severity of illness	Technology Burden	Total Score 0-100	Retrieved 3x/week to coincide with observation		
	EMR	Time in minutes since the end of the last bundled event	With each observation		

	Aim 2. Skin Health (buttocks and chest)			
Acid mantle	рН	0.00 to 14.00.	3x/week with observation	
development				
Water loss	TEWL	TEWL 	3x/week with observation	
	Dermalab			
Skin status	NSCS⁴	NSCS-range 3-9	Twice daily retrieved	
			3x/week	
Microbiome		Microbiota pattern	3x/week with observation	
	Aim 2. Covariates			
	EMR	PMA		
	EMR	Delivery mode		
	EMR	Time since last bath	3x/week with observation	
	EMR	Daily urine output	3x/week with observation	
	EMR	Time in minutes since the last bundled event		

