### 10. Data Analysis and Statistical Considerations

Initially, we will conduct descriptive analyses, including examination of means and proportions and the measures of variability for each variable overall and by bundled care groups. The descriptive analyses will be followed by modeling approaches to respond to the research questions. Tests of statistical significance will be two-sided and the threshold for statistical significance will be P < 0.05.

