## Aim 1. Evaluate differences in infant health when diaper changes occur at 3- versus 6-hours?

**RQ1**. What caregiving activities other than diaper changes are included in bundled care events and do they differ when diaper changes are bundled every 3 versus 6 hours **Analysis:** Each day bundled care is observed, a list of activities will be marked as occurred (1) or did not occur (0). Each infant will have 18 days of data denoting whether an activity occurred or did not occur. Hierarchical clustering of repeated data with an appropriate algorithm that

or did not occur. Hierarchical clustering of repeated data with an appropriate algorithm that producing stable and accurate clusters will be used will be to determine the groupings of activities that occur in the sample. The frequency of the clusters between the intervention groups will be compared.

**RQ2**. Does infant physiological stability ( $\Delta$  heart rate,  $\Delta$  respiratory rate,  $\Delta$  oxygen saturation, # apnea # bradycardias, # desaturations, feeding tolerance) differ between 3- and 6-hour bundled care diapering?

**Analysis:** Heart rate, respiratory rate and oxygen saturation values captured a minute apart for each observed bundled care with a diaper change will be graphically displayed in various constructions to be able to compare the general trends of change in these outcomes between intervention groups, among periods of the bundled care (before, during and after) and over weeks. Further, we will create a daily average of each outcome by period (before, during, and after). Using a repeated measures analysis, we will test for difference among the periods and intervention group and all pairwise period comparisons between groups. PMA and infant illness severity (Technology Burden Score) will be used as a covariate. We will control for multiple comparisons.

A Poisson Generalized linear model for repeated measure will be use to estimate the daily number of apnea, bradycardias, and desaturations events over the 18 days of bundled care observations with a diaper change. The need for a random intercept or slope will be assessed.

 $Log(\# of Apnea Events_{ij}) = b_0 + b_1[I(6HrBC_i)] + b_2(Day_{ij}) + b_3[(I(6HrBC_i)) \times (Day_{ij}) + b_4(PMA_{ij}) + b_5(TechBur_{ij}),$ 

where  $Log((\# of Apnea Events_{ij}))$  is the logarithm of the number of apnea events for individual i at day j.  $b_0$  is the mean log of apnea events for participants who receive 3-hour diaper changes

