and are mean postmenstrual age and with mean technology scores at the start of the study;  $b_1$  is the change in log number of apnea events for those receiving 6-hour diaper changes;  $I(6HrBC_i)$  is an indicator for participants receiving bundled care and 6-hour diaper changes;  $b_2$  is the change in log of the number of apnea events for each day of bundled care;  $Day_{ij}$  is the indicator of the day the number of apnea events was recorded;  $b_3$  is the additional change in log of the number of apnea events over days for those receiving bundled care and 6-hour diaper changes;  $PMA_{ij}$  is the difference from the baseline mean postmenstrual age of the ith participant at the jth day;  $TechBur_{ij}$  is the difference from the baseline mean technology burden score for the ith participant at the jth day;  $b_4$  and  $b_5$  are the expected changes in log number of events for postmenstrual age and technology burden scores, respectively. The estimate of interest is  $b_3$ . The feeding tolerance outcome will be estimated in a similar manner using the appropriate distribution of the outcome and link function for the model.

**RQ3**. Does infant weight gain over time differ between 3- and 6-hour bundled care diapering? **Analysis:** The trajectories of weight measured across the 18 days of bundle care will be fitted using a linear mixed model with a random intercept. We will first determine the best trajectory fit for weight over the 18 days. Once we select an appropriate trend for the data a model similar to the one described below will be estimated.

$$Weight_{ij} = b_0 + b_{i0} + b_1[I(6HrBC_i)] + b_2(Day_{ij}) + b_3[(I(6HrBC_i)) \times (Day_{ij}) + b_4(PMA_{ij}) + b_5(TechBur_{ij}) + \\ \epsilon_{ii},$$

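### The Poisson model for daily apnea, bradycardia and desaturation counts makes no provision for day-to-day overdispersion, so intervals for b3 could be too narrow

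*Combined protocol and SAP*

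**What the plan says.** Section 10, Aim 1 RQ2, sets the model for the three counts: "A Poisson Generalized linear model for repeated measure will be use to estimate the daily number of apnea, bradycardias, and desaturations events". Each infant contributes 18 observed days. The displayed log-linear equation has terms for group, day, group by day, postmenstrual age and technology burden. It contains no random effect and no dispersion parameter. The only flexibility is one further sentence: "The need for a random intercept or slope will be assessed". No rule for that decision is given. The text then adds "The estimate of interest is" b3, the group-by-day coefficient. The opening of Section 10 sets the error rate: "Tests of statistical significance will be two-sided and the threshold for statistical significance will be P < 0.05".

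The plan does not say whether the model is fitted as a mixed model or by GEE, or which kind of standard error is used. It names no check for overdispersion and no fallback. Elsewhere in the same section, the distribution or link is chosen to suit the data for feeding tolerance, the skin condition score and pH. For these three counts, Poisson is fixed in advance.

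**The concern.** A Poisson model sets the variance of an infant's daily count equal to its mean, given the infant and the covariates. If events cluster on bad days, the variance exceeds the mean. A random intercept removes stable differences between infants but leaves this within-infant, day-to-day variation untouched, and that variation governs the precision of a slope contrast such as b3.

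The stake is a confidence interval for b3 that is too narrow, and a nominal 5% test that rejects too often, on each of three outcomes. Section 4.b describes the study as supplying estimates of outcome levels and their variability for a larger trial. A plain Poisson fit has no parameter with which to report the within-infant dispersion that such a trial would need.

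**Working it through.** **Inputs from the documents**
- Two-sided 5% threshold: "Tests of statistical significance will be two-sided and the threshold for statistical significance will be P < 0.05" (Section 10).
- At least 25 infants per arm: the recruitment maximum is set "to ensure at least 25 infants in each study group with complete data" (Section 4.b).
- Days per infant: "The intervention will continue for six weeks" (Section 4.d) and "3x/week for the 3-hour diaper group" (Table 1) give 6 × 3 = 18, which reproduces the 18 days in RQ2.

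**Inputs that are assumed.** The documents give no event rates or variances. The ratio φ = variance/mean within an infant, the mean counts and the spread between infants are all assumptions, shown over a range.

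**Formula.** If the true variance is φ times the mean, the true standard error of b3 is √φ times the model-based one. A test at |z| > 1.96 then has actual size 2[1 − Φ(1.96/√φ)], and the nominal 95% interval covers 100% minus that size. At φ = 1 this returns the plan's 5%. The simulation column has a true b3 of zero, 25 infants per arm, 18 days, means of 1 to 4 events/day, infant intercepts in the model and model-based standard errors.

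| φ | √φ | 1.96/√φ | Size, formula | Coverage | Size, simulation |
|---|---|---|---|---|---|
| 1 | 1.000 | 1.960 | 5.0% | 95.0% | about 4-6% |
| 1.5 | 1.225 | 1.600 | 11.0% | 89.0% | about 10-11% |
| 2 | 1.414 | 1.386 | 16.6% | 83.4% | about 16-19% |
| 3 | 1.732 | 1.132 | 25.8% | 74.2% | about 24-25% |

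In the same simulation, infant-clustered robust standard errors with a small-sample correction and a t reference gave about 4-6%.

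**What the plan's other options would do.** A second simulation (1000 trials per row, 25 per arm, 18 days, true b3 zero) used gamma day-to-day variation with shape k and an infant log-SD of 0.7, and left out postmenstrual age and technology burden. Here φ = 1 + mean/k. Entries are rejection rates for b3; the Monte Carlo standard error is about 0.7 points near 5%.

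| Mean/day | k | φ at that mean | Random intercept | Intercept and slope | Slope kept if likelihood ratio test supports it | Robust GEE, uncorrected |
|---|---|---|---|---|---|---|
| 1 | none | 1 | 4.7% | 3.7% | 4.7% | 7.0% |
| 1 | 4 | 1.25 | 8.2% | 5.9% | 7.1% | 6.6% |
| 1 | 2 | 1.5 | 12.3% | 6.5% | 8.8% | 8.2% |
| 1 | 1 | 2 | 23.5% | 5.8% | 7.7% | 7.0% |
| 4 | none | 1 | 4.3% | 4.0% | 4.2% | 5.7% |
| 4 | 4 | 2 | 23.1% | 7.5% | 8.5% | 8.5% |
| 4 | 2 | 3 | 35.5% | 5.8% | 5.8% | 6.8% |
| 4 | 1 | 5 | 47.2% | 6.5% | 6.5% | 7.4% |

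The random-intercept column exceeds the formula at the same nominal φ because, under this mechanism, infants with higher rates have a larger ratio than the one shown. A plain Poisson GLM with model-based standard errors agreed with that column to within 0.1 point. The two slope columns show that a random slope removes most of the inflation.

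**The case against.** The strongest reply is that the plan already contains the protection. It says the need for a random slope will be assessed, and a slope selected by likelihood ratio test, a natural reading of that sentence, left 5.8-8.8% in the overdispersed rows. A repeated-measures Poisson model can also be fitted by GEE with robust standard errors, and the wording does not exclude that. Both points stand, and they make the concern conditional. They do not remove it, because the plan commits to neither, and a random-intercept fit with model-based standard errors would comply.

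Second, the ratios are assumed, and the technology burden covariate tracks illness severity and could explain some of the bad-day variation. This stands: φ should be read as what remains after covariates, and the documents do not allow it to be estimated.

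Third, robust standard errors are not automatically better. Uncorrected, they gave 6.6-8.5% in the overdispersed rows and 5.7-7.0% with pure Poisson data, so part of the excess reflects having only 50 infants. This is why the correction and t reference matter. The negative binomial option was not simulated; the case for it rests on its having a parameter for the missing variance.

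Fourth, the study is one of estimation, with many outcomes, and Section 10 asks for descriptive measures of variability first. That limits the consequence, but no response to a finding of overdispersion is specified.

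A reader might also infer that an offset for hours observed is needed. Table 1 lists these outcomes as daily counts from the medical record, and nothing in the documents describes partly observed days, so that request is not made.

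**Conclusion.** The point holds in conditional form. The plan fixes Poisson for the three counts and specifies nothing for day-to-day extra-Poisson variation. With model-based standard errors and at most a random intercept, the nominal 5% test of b3 would reject about 11%, 16-19% and 25% of the time at assumed ratios of 1.5, 2 and 3. Intervals would be too narrow by factors of about 1.22, 1.41 and 1.73. With a random slope kept or selected, the rate is about 6-9%.

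A reader might infer that these standard errors will be too small, or that 11-25% is the plan's error rate. The documents support neither: they leave the random effects, estimation method and standard error open, and they give no event rates or variances. This is a cheap improvement to an exploratory analysis, and no confirmatory decision rests on b3.

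**What to change.** For the apnea, bradycardia and desaturation counts, name one of these as the main analysis:

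- a negative binomial mixed model, with its random effects stated in advance; or
- a Poisson model with infant-clustered robust standard errors, a small-sample correction and a t reference.

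The random effects need stating in the first option because true differences in slope between infants also inflate a random-intercept fit. In the second simulation the random-intercept Poisson rate was 13.0% and 33.4% at means of 1 and 4/day, with an assumed slope SD of 0.5 over follow-up and no overdispersion.

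Under either option, report the estimated dispersion for each count, which serves the aim in Section 4.b of estimating variances for a later trial.

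The cost is a few sentences in Section 10 and a standard software option. If there is no overdispersion, the price is one extra parameter or slightly wider intervals. No change to data collection is needed.

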### Infant Exclusion criteria are:

- 1. Neonatal Abstinence Syndrome
- 2. Humidified incubator
- 3. Diaper rash
- 4. Pre-existing or genetic skin conditions
- 5. Severe illness requiring 1:1 nursing care: e.g. minimal stimulation protocol, high frequency ventilation, vasopressor drug support, or body cooling.

Infants will be recruited and enrolled as soon as they meet study criteria (**see Figure 1**. **Study Schemata**). Data collection will begin following study enrollment and will continue until 6 weeks following randomization (**see Table 1**).

Figure 1. Study Schemata

c. Intervention: Infants will be randomly assigned and stratified by birth weight (≤ 800 grams, >800 grams to 1150 grams, > 1150 grams) to either 3- or 6- hour bundled diaper care. All infants will receive bundled care per unit standards until they are eligible for 3-hour bundled care. Infants typically transition to 3-hour bundled care once they are receiving interval feedings every three hours. This transition usually occurs before 3 weeks chronological age in infants >800 grams at birth and by 6 weeks

for infants ≤ 800 grams. Other care activities included in the standard 3-hour bundle vary based upon infant treatment needs, but usually include a diaper change. The only difference in a 3-hour and 6-hour bundled care event will be the timing of the diaper change. Infants will receive a diaper change at either 3 or 6 hours. While 3-hour bundled care is standard of care, this is a clinical environment in which caregiving cannot be expected to occur exactly every three hours to the minute, therefore both expected and actual times for the bundled care events will be collected to include in data analysis as needed. Infants who are receiving the 6-hour bundled diaper care will continue to receive 3-hour care interventions for all other interventions or as dictated by infant care needs. At the 3-hour caregiving interval in which the 6-hour bundled care infants are not due for a diaper change, the nurse will peek into the diaper to ensure there are no stool present. If stool is present, a diaper change should occur and the deviation from the protocol noted in the bedside documentation.

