- vii. Neonatal Skin Condition Score (see Figure 2): The NSCS will be collected twice daily (day and night shift by staff nurses) while infants are participating in the study. The NSCS is a reliable and valid measure of skin condition (Lund & Osborne, 2004)

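### Event counts, feeding tolerance and weight are recorded daily for six weeks, but the models use only the 18 observation days and leave out 24 of 42 without a stated reason

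*Combined protocol and SAP*

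**What the plan says.** **What is recorded.** Table 1 lists the Aim 1 outcomes from the medical record as daily values: "apneic events daily", "bradycardia events daily", desaturation events and feeding tolerance on the same timing, and "Daily weight in grams". The accompanying note that they are retrieved three times a week says how often staff read the chart, not how often the value exists.

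**For how long.** Section 4d: "The intervention will continue for six weeks at which time collection of data will stop". Section 4b likewise says that data collection "will continue until 6 weeks following randomization".

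**What is modelled.** In section 10, Aim 1 RQ2, the repeated-measures Poisson model covers "events over the 18 days of bundled care observations with a diaper change". Feeding tolerance is to be handled in a similar manner. For RQ3: "The trajectories of weight measured across the 18 days of bundle care will be fitted", using a linear mixed model with a random intercept. In both models the estimate of interest is b3, the group-by-day interaction. Both adjust for postmenstrual age (PMA) and the Technology Burden score. Table 1 schedules Technology Burden three times a week, to coincide with observation.

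**The concern.** Restricting an analysis to observed care with a diaper change makes sense for minute-by-minute vital signs around that event, and the three-times-weekly schedule is all there is for TEWL, pH and swabs. It has no evident purpose for a 24-hour event count or a daily weight, which exist whether or not an observer came that day. The plan gives no reason for the limit and plans no model on all days.

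What is at stake is precision. Section 4b sets the goal as estimating outcome values, their variances and their change over time, with at least 25 infants per group with complete data. In a study of that size and purpose, leaving out recorded days widens the interval for b3, the quantity that RQ2 (counts) and RQ3 are meant to estimate.

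**Working it through.** **1. The plan's own figure.** Three observation days a week × 6 weeks = 18, as stated. The fourth weekly observation in the 6-hour group (section 10, RQ4) is compared with a diaper change on the same day, so it adds no day; 4 × 6 = 24 would not give 18. The RQ3 text does not use the word observation, but only the observation schedule yields 18.

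**2. Days left out.** 7 × 6 = 42 recorded days; 42 − 18 = 24; 24/42 = 57%. A shorter stay loses the same share (16 of 28 days at 4 weeks, 8 of 14 at 2 weeks). With 25 infants per group completing six weeks, 50 × 18 = 900 infant-days are modelled out of 50 × 42 = 2,100.

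**3. Effect on the standard error (SE) of b3.** The documents give no event rates or variances, so the following are assumptions: observation on days 0, 2 and 4 of each week, a constant daily rate, days independent given the infant, and 25 infants per arm. Let Sxx be the sum of squared centred days: 2,620.5 for the 18 days and 6,170.5 for all 42.

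Per-infant slope variance is v = (between-infant slope variance) + (residual variance)/Sxx, and SE(b3) = √(2v/25). The factor 2/25 cancels in the ratio SE(42 days)/SE(18 days).

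*Common slope (counts or weight):* √(2,620.5/6,170.5) = 0.65, a 35% reduction. This is the best case.

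*Counts, log-slope SD 0.02 per day (variance 0.0004), residual term 1/(rate × Sxx):*

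| Events/day | v, 18 days | v, 42 days | SE ratio |
|---|---|---|---|
| 0.2 | 0.001908 + 0.0004 = 0.002308 | 0.000810 + 0.0004 = 0.001210 | 0.72 |
| 3 | 0.000127 + 0.0004 = 0.000527 | 0.000054 + 0.0004 = 0.000454 | 0.93 |

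Over a wider grid (log-slope SD 0.01 to 0.04, 0.5 to 5 events/day) the ratio runs from 0.70 to 0.99.

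*Weight, residual SD 40 g (variance 1,600):*

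| Slope SD, g/day | v, 18 days | v, 42 days | SE ratio |
|---|---|---|---|
| 2 | 0.611 + 4 = 4.611 | 0.259 + 4 = 4.259 | 0.96 |
| 4 | 0.611 + 16 = 16.611 | 0.259 + 16 = 16.259 | 0.99 |

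If infants instead share a slope but daily residuals are autocorrelated (AR(1), correlation 0.3 to 0.95), the weight ratio is 0.81 to 0.96.

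**4. What happens if days are added to the weight model with only a random intercept.** Such a model puts the slope variation into the residual and treats it as independent noise. With n days per infant, its residual variance is about 1,600 + (slope variance) × Sxx/(n − 1), and its reported per-infant slope variance is that divided by Sxx. With no true group difference, the two-sided 5% test then rejects with probability 2 × [1 − Φ(1.96 × √(reported/true v))].

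- Slope SD 2 g/day, 18 days: reported 0.846, true 4.611, false-positive rate about 40%.
- Slope SD 2 g/day, 42 days: reported 0.357, true 4.259, about 57%.
- Slope SD 4 g/day: about 55% with 18 days and about 69% with 42.

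So the days and the random-effects structure have to be changed together.

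**The case against.** The strongest reply is that 57% of the days is not 57% of the information. The 18 days already span all six weeks, so b3 still refers to the whole period. Once infants differ in their own slopes, extra days per infant add little: the gain is 7% for counts at 3 events/day and 1% to 4% for weight. The descriptive analyses in section 10 are not limited to 18 days either, so the other records are not wholly ignored. All of this stands and bounds the size of the point. A worthwhile gain remains for rare events.

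The 18 days are also the days on which Technology Burden is scheduled, which may explain the restriction, although the plan does not say so. This stands as a cost: an all-days model needs that covariate from somewhere.

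A reader might infer two stronger points that the documents do not support.

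- *That the skin condition score is restricted in the same way.* For that score, "The NSCS will be collected twice daily" (section 4e.vii), and Aim 2 RQ2 takes the apnea model as its pattern. But RQ2 borrows the form of the model and states no 18-day limit.
- *That observation days are unrepresentative and bias the comparison.* Skin measurements do fall on those days, but section 8 says handling will be kept to a minimum, and both arms are observed on three days a week. The 6-hour arm has one extra observed event per week, on one of those same days. Nothing in the documents shows that events differ on observation days, or differ by arm.

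**Conclusion.** The point holds as one of efficiency. For apnea, bradycardia, desaturation and weight, section 10 limits the models to 18 of 42 recorded days without a reason; feeding tolerance follows by reference to the count model. The cost is precision in b3. Using all days would cut its SE by about 28% for counts near 0.2 per day and about 7% near 3 per day (log-slope SD 0.02), by at most 35% with a common slope and independent days, and by only 1% to 4% for weight if slopes vary by 2 to 4 g/day. These percentages rest on assumed rates, variances and spacing; the count of 24 in 42 days assumes only that the infant completes six weeks. No bias and no wrong conclusion is shown. It should be changed because the remedy is cheap, provided the random slope comes with it.

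**What to change.** In section 10, Aim 1 RQ2 (event counts and feeding tolerance) and RQ3 (weight):

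1. Replace the 18 days with all recorded days from randomisation to the end of the six-week intervention, and define Day as elapsed days since randomisation.
2. Include a random slope for day as well as the random intercept. RQ2 already says that the need for one will be assessed. For weight it is essential, because RQ3 has a random intercept only and extra days would then add false precision.
3. Compute PMA for each day. Either extract Technology Burden daily or use the nearest recorded value, and state which.
4. Keep the 18-day analysis as a sensitivity analysis, or add an observation-day indicator, so that any difference between observation days and other days can be seen.

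Leave the three-times-weekly schedule as it is for vital signs, TEWL, pH and swabs.

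The cost is an amendment to the analysis text plus either extra chart extraction for Technology Burden or carried covariate values on the added days. No additional contact with infants is needed.

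### The apnea, bradycardia and desaturation analysis names only the arm-by-day slope as its estimate, so a rate ratio constant from the first day is not tested

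*Combined protocol and SAP*

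**What the plan says.** In section 10, Aim 1, RQ2 asks whether heart rate, respiratory rate, oxygen saturation, the three event counts and feeding tolerance differ between arms (the question ends "feeding tolerance) differ between 3- and 6-hour bundled care diapering"). Unlike RQ3 on weight gain, it contains no wording about change over time.

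For the counts, a repeated-measures Poisson model is to be used "to estimate the daily number of apnea, bradycardias, and desaturations events". Its terms are arm (b1), Day (b2), arm × Day (b3), postmenstrual age (b4) and Technology Burden (b5).

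- b1 "is the change in log number of apnea events for those receiving 6-hour diaper changes".
- b3 is "the additional change in log of the number of apnea events over days for those receiving bundled care and 6-hour diaper changes".

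The paragraph then states "The estimate of interest is" b3, and says that feeding tolerance will be handled in a similar way.

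The vital signs, in the same RQ2, are treated differently: "we will test for difference among the periods and intervention group and all pairwise period comparisons between groups". The sentence "We will control for multiple comparisons" stands in that vital-sign paragraph, not with the counts. The opening of section 10 promises descriptive work for every variable: "examination of means and proportions and the measures of variability for each variable overall and by bundled care groups".

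**The concern.** The question is about level and the named estimate is about slope. The only between-arm quantity designated for the counts says whether the arms drift apart as days pass. It does not say whether one arm has more events than the other.

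A prompt and sustained effect is plausible here. The diapering schedule differs between arms from the first day of the intervention (section 4c), and the rationale in section 3 is that a diaper change can itself be stressful. Such an effect, if constant on the ratio scale, would leave b3 at zero. A null b3 could then be reported as no difference in apnea, bradycardia or desaturation when one arm had a sustained excess.

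Section 4b says that the study is meant to inform a larger one. The average rate ratio with its confidence interval, which that study would need, is not pre-specified.

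**Working it through.** **Inputs from the documents.** At least 25 infants per arm with complete data (section 4b); 18 observation days per infant, which is 3 per week × 6 weeks (section 10); two-sided 0.05 (section 10); the Poisson model as printed. The documents state no power, event rate or variance, so there is no figure of theirs to reproduce.

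**Structural result, with no assumed rates.** At equal covariates,

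log rate ratio on day t = b1 + b3 × t.

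A rate ratio RR that is the same on every day requires b1 = ln(RR) and b3 = 0. For RR = 0.5, b1 = −0.693 and b3 = 0. The equation contains no pre-randomisation count, so b3 cannot stand in for a change from baseline.

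**Illustration by simulation.** All rates and variances here are assumed.

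- Base case: about 3 events/day, between-infant log-SD 0.7, observation on days 1, 3 and 5 of each week (mean day 20.5).
- Covariates: baseline postmenstrual age SD 2 weeks with log-rate −0.10 per week; Technology Burden SD 12 between and 5 within infants, falling 0.3/day, with log-rate +0.02 per point.
- Analysis: exchangeable Poisson GEE, Mancl-DeRouen standard errors, t with 44 df, 2,000 replicates.
- Average contrast: b1 + b3 × 20.5.

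| Constant rate ratio | b3 rejects | Average contrast rejects |
|---|---|---|
| 0.7 | 5.1% | 31% |
| 0.6 | 5.1% | 58% |
| 0.5 | 5.2% | 80% |
| 1.67 | 5.7% | 57% |

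**Sensitivity.**

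- Five assumption sets (0.5 to 3 events/day, log-SD 0.5 to 1.0, with and without a random slope): b3 rejects in 4.2–6.1%. The average contrast rejects in 18–43%, 32–73% and 50–92% for rate ratios 0.7, 0.6 and 0.5.
- Random-intercept Poisson model, base case: average contrast 43%, 69% and 90%; b3 4–5%.
- Smaller between-infant spread (log-SD 0.3 or 0.6; baseline rate parameter 0.5, 2 or 5 events/day; Technology Burden omitted; 300 runs each): b3 2.7–7.0%; average contrast 38–95% at 0.7 and 88–100% at 0.5.

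The power of the average contrast moves a great deal with the assumptions. The b3 result does not.

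**Opposite case.** Let the rate ratio grow from 1 to 0.6 by day 42. Then b3 = ln(0.6)/42 = −0.0122 per day, and the rate ratio at day 20.5 is exp(−0.0122 × 20.5) = 0.78. In the base case b3 rejects in 92%. Over the five sets b3 gives 29–92% and the average contrast 12–23%. Each estimate misses what the other sees.

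**Limit of the claim.** Take a constant difference of 0.75 events/day while the control rate falls from 3 to 1.5. As a reduction, the ratio moves from 2.25/3 = 0.75 to 0.75/1.5 = 0.50, so b3 is not zero. Simulated without covariates, b3 gives 48% and the average contrast 46%.

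**Precision.** In the base case the SE of the average log rate ratio is 0.24. An estimate of 0.6 has 95% CI 0.6 × exp(±2.015 × 0.24) = 0.37 to 0.97.

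**Related minor gap: skin outcomes at week 6.** The Aim 2 questions on TEWL, NSCS and pH ask about the end of 6 weeks, but their analysis paragraphs name no week-6 estimate. One is obtainable. Under a linear trend with a random intercept, in SD units,

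SE = √{2/25 × [ICC + (1 − ICC) × (1/18 + (40 − 20.5)²/2620.5)]},

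which is 0.188, 0.219 and 0.247 for assumed ICCs of 0.3, 0.5 and 0.7. Power for a 0.8 SD difference is 99%, 95% and 89%; for 0.5 SD it is 74%, 61% and 51%.

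**The case against.** The best defence is that the information is not lost. b1 is defined and fitted, the model is described as estimating daily numbers, and group means will be tabulated. In the base case b1 as printed (the contrast at Day 0) has 29%, 54% and 79% power, close to the average contrast. Section 4b also lists change over time among the study's goals, and the study is exploratory with no stated power. Finally, section 4b has data collection start after enrolment, which could be read as allowing pre-randomisation data.

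Much of this is fair, and it narrows the point: what is missing is a designated contrast and its test, not a term in the model. It does not remove the point.

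- The group summaries are descriptive; the modelling is what section 10 says will answer the research questions, and there b3 is the estimate named.
- b1 depends on how Day is coded. At 0.5 events/day it loses power against the average contrast: 29%, 51% and 76% against 43%, 73% and 92%. Turning to it after a null b3 would be a post hoc choice.
- The goal in section 4b covers values and variances as well as their change over time.
- Section 4d places the start of data collection at randomisation, and no baseline count enters the equation in any case.

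Two further cautions stand. The power figures depend on assumed rates and variances. An average over observed days is ill-defined when follow-up is incomplete, so a fixed reference day is preferable.

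**Conclusion.** The concern holds. For apnea, bradycardia and desaturation counts the plan names only the slope difference, while RQ2 asks whether the arms differ. Under the printed model, a rate ratio constant from the first day is detected by b3 only at about the 5% error rate, whatever its size. That follows from the model and needs no assumed rates.

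How much power a level contrast would add cannot be fixed from the documents. In the base case it is 31–80% for rate ratios 0.7 to 0.5, and the figure varies widely with the assumed rates and spread.

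The claim is confined to effects constant on the ratio scale. b3 remains right for effects that build over time and for weight gain in RQ3. Feeding tolerance is affected only by inference, because it is to be modelled similarly. This should be fixed before the data are analysed.

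**What to change.** In section 10, Aim 1 RQ2, name two estimates of interest for each event count:

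- the between-arm rate ratio averaged over the six weeks, as b1 with Day centred at a fixed mid-follow-up day (equivalently b1 + b3 × mean Day);
- b3.

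Report both with 95% confidence intervals. Use the corresponding average contrast for feeding tolerance on its own link scale. State how multiplicity is handled for the counts, for example Holm across the two estimates within each outcome; this does not address multiplicity across outcomes. Leave b3 as the estimate for weight gain. For TEWL, NSCS and pH, add the model-based group difference at week 6 from whichever trajectory is chosen.

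The cost is one or two sentences, one more named estimate per outcome and no new data. If Holm is used, base-case power of the average contrast falls from 31%, 58% and 80% to 21%, 45% and 73% (rate ratios 0.7, 0.6 and 0.5), and power of b3 for the growing effect falls from 92% to 87%.
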